7.4.4 Removal of Subjects From Therapy or Assessments

Subjects may stop study agent and withdraw from the study for any of the following reasons:

- Subject request
- Use of nonpermitted concurrent therapy
- Non-compliance with the study agent or study schedule
- Lost to follow-up
- Occurrence of AEs not compatible with the continuation of subject participation in the study, in the investigator's opinion, or unacceptable to the subject to continue
- Investigator request
- Intercurrent illness
- Sponsor request
- Pregnancy

Subjects who do not comply with the protocol or who withdraw consent will be replaced. Subjects who stop study agent for any other reason (ie, AE) will not be replaced.

Subjects are free to withdraw from the study at any time without providing reason(s) for withdrawal and without prejudice to further research treatment. The reason(s) for withdrawal will be documented in the case report form (CRF).

Subjects withdrawing from the study will be encouraged to complete the same final evaluations as subjects completing the study according to this protocol, particularly safety evaluations. The aim is to record data in the same way as for subjects who completed the study.

Reasonable efforts will be made to contact subjects who are lost to follow-up. These efforts must be documented in the subject's file.

The sponsor has the right to terminate the study at any time in case of SAEs or if special circumstances concerning the study agent or the company itself occur, making further research treatment of subjects impossible. In this event, the investigator(s) will be informed of the reason for study termination.

Pregnancy

Only female subjects with negative pregnancy tests will be allowed to enroll in the study. Subjects will be instructed that known or suspected pregnancy occurring during the study in female subjects should be confirmed and reported to the investigator, who will then withdraw the subject from the study without delay. Upon discontinuation from the study, only those procedures that would not expose the subject to undue risk will be performed.

The investigator should also be notified of pregnancy occurring during the study but confirmed after completion of the study.

In the event that a subject is subsequently found to be pregnant after inclusion in the study, any pregnancy will be followed to term, and the status of mother and child will be reported to the sponsor after delivery.

Full details will be recorded on the withdrawal page of the CRF, or an SAE report will be completed if the subject has completed the study. Procedures to be followed if a pregnancy occurs are provided in [Section 9.1.2.2.1](#).

7.4.5 Enrollment Guidelines

All eligibility requirements must be reviewed before the subject may enter the study. The following information must also be provided to the sponsor and/or their representative, as requested:

1. Completed and signed protocol-specific eligibility checklist.
2. All pages of the original signed informed consent forms (ICFs), including Health Insurance Portability and Accountability Act (HIPAA)²¹ Form for US sites.

3. Relevant source documents such as: subject medical history and physical exam, admission or discharge notes, diagnostic reports, confirmation of diagnosis, and relevant subject-specific written communication.

7.5 Investigational Products

7.5.1 Investigational Products Administered

7.5.1.1 NH002

Each subject will receive 1 of 3 NH002 doses (2.5 μ l/kg, 5.0 μ l/kg, or 10.0 μ l/kg) by IV bolus injection. The subjects will be allocated sequentially to each single dose as follows: initial 12 subjects receive 2.5 μ l/kg, the next 12 receive 5.0 μ l/kg, and final 12 receive 10.0 μ l/kg. See [Table 4](#).

Table 4: NH002 Administration

| Agent | Subjects | Dose (μ l/kg) IV bolus | Schedule |
|-------|-----------------|-----------------------------|----------|
| NH002 | First set of 12 | 2.5 | Day 1 |
| | Next set of 12 | 5.0 | |
| | Final set of 12 | 10.0 | |

7.5.1.2 Stopping Criteria for Dosing

All AEs will be evaluated during the successive cohorts of subjects, per dose level. Intrasubject dose escalations are not permitted.

Dose escalation will proceed successively with each cohort as described in previous sections ([Section 7.5.1.1](#)), unless any of the following criteria is/are exhibited:

- The occurrence of any SAE considered at least possibly related to study agent administration in any 1 subject who received study agent. The occurrence of such an SAE will supersede all other stopping rules.
- The occurrence of the following in 30% of subjects (within any one of the 3 dose levels):
 - moderate or severe clinically significant nonhematologic lab toxicity, including cardiac disorder(s)
 - moderate or severe clinically significant hematologic lab toxicity
 - mild, moderate, or severe clinically significant anaphylactic reaction

Supportive care is permissible at the discretion and clinical judgment of the treating investigator, until symptoms are resolved to baseline.

If any of the stopping criteria for dosing are observed, the study will be halted, and the risk to other subjects evaluated, prior to a decision as to whether to terminate the study (See also [Section 9.1.2.1](#) for overall study stopping rules).

Proceeding to the next dose level is permissible before completion of a cohort when no visible contrast effect and no safety concerns are observed in 4 subjects in a cohort. Such decision will be triggered by the sponsor in conjunction with the DEC, and as approved by the appropriate regulatory agencies.

A more conservative dose assignment, evaluation of an intermediate dose, and/or expansion of an existing dose level is permissible if such measures are needed for patient safety or for a better understanding of NH002 dose-related toxicity, and/or exposure. Such changes will be determined by the sponsor in conjunction with the DEC, and as approved by the appropriate regulatory agencies.

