9.1.2.2 Adverse Events

Adverse Event Definition

An AE is defined as any untoward medical occurrence in a clinical study subject administered a medicinal product which does not necessarily have a causal relationship with this treatment. An AE can therefore be any unfavorable and unintended sign (including an abnormal laboratory finding), symptom, or disease temporally associated with the use of a medicinal (investigational) product, whether or not it is related to the medicinal (investigational) product. This includes an exacerbation of pre-existing conditions or events, intercurrent illnesses, drug interaction or the significant worsening of the indication under investigation that is not recorded elsewhere in the CRF under specific efficacy assessments. Anticipated fluctuations of pre-existing conditions, including the disease under study, that do not represent a clinically significant exacerbation or worsening need not be considered AEs.

It is the responsibility of the investigator to document all AEs that occur during the study. Any AEs will be elicited by asking the subject a nonleading question, for example, "Have you experienced any new or changed symptoms since we last asked/since your last visit?". All AEs should be reported on the appropriate page of the CRF.

Assessment of Severity

Each AE will be assigned a category by the investigator as follows:

Mild: An AE that is easily tolerated by the subject, causes minimal discomfort,

and does not interfere with everyday activities.

Moderate: An AE that is sufficiently discomforting to interfere with normal everyday activities; intervention may be needed.

Severe: An AE that prevents normal everyday activities; treatment or other intervention usually needed.

If there is a change in severity of an AE, it must be recorded as a separate event.

Assessment of Causality

Every effort will be made by the investigator to assess the relationship of the AE, if any, to the study agent. Causality should be assessed using the categories presented in the following:

Unrelated: Clinical event with an incompatible time relationship to study agent administration, and that could be explained by underlying disease or other drugs or chemicals or is incontrovertibly not related to the study agent.

Unlikely: Clinical event whose time relationship to study agent administration makes a causal connection improbable, but that could plausibly be explained by underlying disease or other drugs or chemicals.

| | |

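### The 30% stopping rule counts only moderate or severe laboratory toxicity, but the only severity scale grades by interference with daily activities, so symptom-free laboratory changes grade as mild or are graded inconsistently.

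*Protocol*

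**What the plan says.** Protocol Section 7.5.1.2 lists what stops escalation. Apart from a possibly related SAE in any one subject, the trigger is "The occurrence of the following in 30% of subjects (within any one of the 3 dose levels" of any of three kinds of toxicity:

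- a first limb for laboratory findings other than blood counts, which also takes in the heart: "moderate or severe clinically significant nonhematologic lab toxicity, including cardiac disorder(s";
- a second limb, with the same lower bound on severity, for blood counts: "moderate or severe clinically significant hematologic lab toxicity";
- a third limb for allergic events, with no lower bound on severity: "mild, moderate, or severe clinically significant anaphylactic reaction".

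Mild events count in the third limb but not in the first two. Cohorts are of 12: "initial 12 subjects receive 2.5 μ l/kg, the next 12 receive 5.0 μ l/kg, and final 12 receive 10.0 μ l/kg" (Section 7.5.1.1).

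Section 9.1.2.2 defines severity. An abnormal laboratory finding is an adverse event: "An AE can therefore be any unfavorable and unintended sign (including an abnormal laboratory finding". The scale is general: "Each AE will be assigned a category by the investigator as follows". Mild means well tolerated, with little discomfort and no effect on daily activities. Moderate is "An AE that is sufficiently discomforting to interfere with normal everyday activities; intervention may be needed". Severe means that normal activities are prevented and that treatment or another intervention is usually needed.

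The Synopsis (Treatment) and Section 7.1 add that, if the stopping criteria are met in a cohort, the previous dose becomes the maximum tolerated dose.

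**The concern.** Two of the three toxicity limbs depend on grading a laboratory result as moderate or severe, and the scale provided does not grade laboratory results by anything measured in the laboratory. It asks how the subject feels and functions. A change in troponin, transaminases, creatinine or platelets may be large and cause no symptoms.

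The schedule makes this more than a matter of wording. CBC, coagulation, chemistry and troponin I are sampled in all subjects regardless of symptoms, at up to 240 minutes after dosing, during on-site observation. Later follow-up is two telephone calls with no laboratory tests (Section 8.3). Symptom-free changes are therefore what this sampling is likely to find, and interference with everyday activities is hard to judge in that setting.

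At stake is whether the pre-specified trigger responds to laboratory toxicity, and whether it responds in the same way at every site of a multicenter study that uses local laboratories.

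**Working it through.** The plan has no figure to reproduce: Section 10.8 says that no formal sample size calculation was required, and no operating characteristics are given for the stopping rule. The check is of definitions first, then an illustration.

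**Step 1: apply the scale to the rule.** Take a clinically significant laboratory change without symptoms.

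- Is it an adverse event that must be graded? Yes, under the definition and grading instruction in 9.1.2.2.
- Is it moderate? That requires discomfort enough to interfere with activities. Not met.
- Is it severe? That requires normal activities to be prevented. Not met.
- Is it mild? It fits.
- Does mild count in the two laboratory limbs? No.

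**Step 2: look for another scale.**

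- Protocol 9.1.2.2.3 uses local reference ranges to judge clinical significance and pathological change, not severity.
- SAP 5.3.2.1 and 5.3.2.2 flag values as low or high and produce shift tables.
- SAP 5.3.1 summarises events by severity but introduces no new scale.
- SAP 5.3.6 classes ECGs as normal, abnormal not clinically significant, or abnormal clinically significant.

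None of these is a severity grade for a laboratory value.

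**Step 3: the threshold.** 0.30 × 12 = 3.6. Since 3/12 = 25.0% falls short and 4/12 = 33.3% does not, a full cohort needs at least 4 subjects.

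**Step 4: illustration.** Let p be the assumed true proportion of subjects with clinically significant laboratory toxicity that the rule is meant to count. Let f be the assumed share of it that can be graded moderate or severe. The documents give neither. With independent subjects and a full cohort, the number counted is Binomial(12, q) with q = p × f, and

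P(rule fires) = 1 − Σ C(12,k) q^k (1−q)^(12−k), summed over k = 0 to 3.

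For p = 0.30 and f = 1, q = 0.30 and the sum is 0.0138 + 0.0712 + 0.1678 + 0.2397 = 0.4925, so P = 0.5075. The other values follow in the same way:

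| Assumed p | f = 1 | f = 0.5 | f = 0.25 | f = 0 |
|---|---|---|---|---|
| 0.2 | 0.205 | 0.026 | 0.002 | 0 |
| 0.3 | 0.508 | 0.092 | 0.010 | 0 |
| 0.4 | 0.775 | 0.205 | 0.026 | 0 |
| 0.5 | 0.927 | 0.351 | 0.053 | 0 |

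The f = 0 column is the literal reading when all the toxicity is symptom-free.

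**The case against.** A reader might infer that symptom-free laboratory toxicity can never count, so that two limbs of the rule are dead. The documents do not support that as a flat statement. Section 7.5.1.2 does not cross-refer to the scale in 9.1.2.2, and it evidently expects laboratory toxicity to be able to reach moderate or severe. The moderate and severe definitions also mention intervention, so an investigator might grade a treated but symptom-free abnormality above mild. This stands in part. The intervention wording accompanies the activity criterion and does not replace it, so it leads to grading that may differ between investigators, not to a usable scale.

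A reader might also infer that large laboratory changes would pass unnoticed, or that the DEC's decision rests on this grading. That is not supported either:

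- The DEC reviews clinical, laboratory and ECG data after the first and the last subject of each cohort, and can recommend stopping on any safety concern (Sections 7.1 and 9.2).
- Section 9.1.2.1 provides for dosing to be halted while the DEC considers termination for safety concerns.
- The Synopsis makes enrolment of the next cohort conditional on no serious adverse reactions or toxicity reactions having been observed, with no severity grade attached.
- The SAP plans listings of abnormal values and shift tables, and tables and listings by cohort for the DEC.

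Nor does the maximum tolerated dose rest on the trigger alone, since Section 10.6 also refers to selection rules based on efficacy and safety.

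Finally, the separate DEC Charter is not among the documents and may contain a laboratory scale. Section 9.2 describes it as covering timelines and responsibilities, and neither document refers to it for grading, but its contents can be neither confirmed nor excluded.

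These safeguards limit the consequence. They are discretionary or expressed in other terms, and they do not supply the missing grade for the pre-specified 30% rule.

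**Conclusion.** The point holds in limited form. Section 7.5.1.2 uses a severity grade that the only scale in the protocol and SAP does not supply in a usable way for laboratory findings. Read literally, symptom-free changes add nothing to the 4 of 12 needed; read generously, the result depends on the investigator.

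The effect is on the automatic 30% trigger for the two laboratory limbs, and on the maximum tolerated dose where that trigger sets it. The related-SAE criterion, the anaphylaxis limb, symptomatic cardiac disorders (which can be graded on the existing scale) and the DEC's general review and power to halt are unaffected.

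At an assumed true rate of 30%, the chance that the rule fires falls from 0.51 when all such toxicity can be graded moderate or severe to 0.09, 0.01 and 0 when a half, a quarter or none can. These figures rest on assumed rates and shares, independent subjects, a full cohort of 12, and reading the rule as at least 30%. The conflict between the two sections does not depend on them.

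**What to change.** Reconcile Sections 7.5.1.2 and 9.1.2.2 by stating, before first dosing, which severity scale applies to the two laboratory limbs. If the DEC Charter already holds such a scale, a cross-reference in 7.5.1.2 is enough. The choice of scale and any thresholds belongs to the sponsor and the DEC; none is proposed here.

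Add to the DEC shells (SAP Section 5.6) one table giving the number and percentage of subjects who meet each limb of the stopping criteria, by dose. No table listed in the SAP gives this count.

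The cost is a short protocol clarification and one table. No new data are needed, since the laboratory values and local reference ranges are already collected.

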7.5.1.3 Microspheres and Contrast Agent Activation

NH002 is a contrast agent which is intended for administration only after activation in the designated apparatus. Before injection, the product must be activated and prepared according to outlined instructions. The contrast agent will be prepared and administered by designated pharmacy technician(s), study nurse(s), sonographer, or radiologist.

An activation device provided by Trust Bio-sonics, Inc., TRANSMIXTM, should be used as a companion to NH002 for microbubble activation. TRANSMIXTM is equipped [REDACTED] and a mechanical agitator for the enhanced mixing of the lipids solution and C₃F₈ for gas encapsulation.

[REDACTED] Refer to the [TRANSMIX User's Guide](#) for further details.

Immediately after activation, the activated contrast agent appears as a milky white suspension and should be used immediately. If the product is not used within 5 minutes after activation, the contrast agent should be resuspended by 10 seconds of hand agitation by inverting the vial, before the product is withdrawn in a syringe.

Invert the vial and withdraw the activated milky white suspension using an 18- to 20-gauge syringe needle. Withdraw the material from the middle of the liquid in the inverted vial. Do not inject air into the vial.

Use the product immediately after its withdrawal from the vial; do not allow the product to stand in the syringe.

For single use only: NH002 does not contain bacterial preservative(s). Bacterial contamination with the risk of post-administration septicemia can occur following the puncture of the

elastomeric septum. It is essential to follow directions for activation carefully and to adhere to strict aseptic procedures during preparation.

7.5.1.4 Injection Volume(s)

The injection volume (μl) for each subject will be calculated based on their body weight (kg). See [Table 5](#).

Table 5: NH002 Injection Volume(s)

| NH002 Dose ($\mu\text{l}/\text{kg}$) | NH002 volume (μl) based on subject weight (X kg) |
|--|---|
| 10.0 | = X \times 10.0 |
| 5.0 | = X \times 5.0 |
| 2.5 | = X \times 2.5 |

7.5.1.5 Injection Route and Rate

For this trial, NH002 must be injected by an IV bolus method. **Do not administer by intra-arterial injection.**

Slow injection is important for safety (according to prior experience in animal studies). **Sites should always have cardiopulmonary resuscitation personnel and equipment readily available before administration and monitor all subjects for acute reactions.**

NH002 will be injected as an IV bolus, within 30 to 60 seconds, followed by a 10 mL saline flush over 10 seconds.

7.5.1.6 Emergency Event Management

Subjects will be closely monitored by a medical team during the injection and for at least 4 hours (240 minutes) following dosing for the presence of symptoms of allergic or hypersensitivity reaction(s). Subjects who receive 4-hour monitoring after the dose on Day 1 will be encouraged to quickly report any symptoms at the time during this period. The necessary rescue material, equipment, and appropriate medications will be available in the clinic to allow rapid intervention in case of emergency.

7.5.2 Identity of Investigational Products

7.5.2.1 NH002 (perflutren lipid microspheres) Injectable Suspension

Formulation, Dosage and Strength

[figure not shown]
The gas core in NH002 is perflutren. The structure is a gas core surrounded by a lipid shell ([Figure 6](#)). NH002 is formulated as a microbubble injectable suspension of perflutren in single-use, 1-mL lipid solution in 2-mL vials with [REDACTED] C₃F₈ in headspace for IV administration.

Chemical Name

NH002 (perflutren lipid microspheres)

Chemical Structure

Molecular formula: C₃F₈

How Supplied

NH002 is supplied as a single use, 1-mL lipid solution in 2-mL clear glass vial containing clear liquid in packages of 4 single-use vials.

Storage and Handling

Store NH002 between 2-8°C (36°-46°F).

Source

Trust Bio-sonics (TRUST) will supply NH002 (and the associated TRANSMIX™ apparatus). The study agent will be manufactured and imported according to the relevant regulatory requirements.

Trust Bio-sonics (TRUST) Address: [name]
[name]
Taiwan (R.O.C.)
[contact]

[figure not shown]
7.5.3 Packaging and Labeling

7.5.3.1 NH002

All packaging and labeling operations will be performed according to Good Manufacturing Practice for Medicinal Products and the relevant regulatory requirements. NH002 sample label is provided in [Figure 7](#).

Figure 7: NH002 Sample Packaging Label

7.5.4 Selection of Doses in the Study

Refer also to [Section 5](#) (Introduction).

7.5.5 Selection and Timing of Dose for Each Subject

On the day of dosing, each subject will receive one injection (of NH002), as per [Section 7.5.1](#).

Up to 36 eligible subjects will be assigned with *sequential allocation* to 1 of 3 doses of NH002 (2.5 µl/kg, 5.0 µl/kg, or 10.0 µl/kg IV bolus).

No dose adjustments will be permitted, per protocol. There are no restrictions on the time of day of dosing. There are also no restrictions in relation of dosing to meals.

7.5.6 Prior and Concomitant Therapy

There is no specific known evidence of contraindications between the ingredients of NH002 and other prior and concomitant therapy. Concomitant medications and therapies will be recorded beginning at the time of screening, as well as during and after research treatment.

7.5.6.1 Prohibited Medication/Therapy

Subjects must not have received an investigational compound within 30 days before enrolling in the study. Subjects must also not have received any contrast agent either intravascularly or orally within 48 hours before NH002 administration. Concomitant medications and procedures will be recorded beginning at the time of screening, as well as during and after research treatment.

Subjects with known right-to-left, bidirectional, or transient right-to-left cardiac shunt(s) are **excluded** from this study, but it is important to note the following: When administering NH002 to subjects with a cardiac shunt, the microspheres can bypass filtering by the lung and enter the arterial circulation. Subjects with shunts should be assessed for embolic phenomena following NH002 administration.

7.5.6.2 Rescue Medication

Slow injection is important for safety (according to prior experience in animal studies). Sites should always have cardiopulmonary resuscitation personnel and equipment readily available before administration and monitor all subjects for acute reactions.

7.5.7 Dosing Compliance

On the day of scheduled dosing (ie, Day 1) dosing compliance will be assessed by the administering clinician(s). At a minimum, date, time, duration, and dose should be recorded in the treatment record(s) to confirm that each dose of NH002 was administered as per protocol.

